#### 1.3.4.6 Cessation Buprenorphine Dose

In the BBORN trial, the cessation dose was within 10% of the initial dose. The mean dose at time of cessation was 5.3 mcg/kg, based upon actual weight at the time of cessation. No infants required readmission following discharge, however 44% required a rescue dose after scheduled dosing was completed. The current trial will define the cessation dose as the dose that is equal or less than the initial dose in mcg (and not a weight normalized dose of mcg/kg). Most infants will regain their birthweight at about the time for cessation. A simulation was performed to estimate the impact of the proposed cessation dose (Table 8). This simulation was based upon cessation of all dosing at the cessation dose without any extension of interval. Despite a higher cessation dose, the model predicted less of a need for rescue doses. Symptom driven administration of rescue doses ensure that there will not be inadequate treatment of symptoms, even if the precision of the modeled response is less than expected.

Table 8: Simulated Time to Wean (hours) with Varied Wean Rate

	BPHORE	BBORN
Initial dose (mcg/kg)	8	5.3
Cessation dose	$\leq 100\%$ of the initial dose	$\leq 110\%$ of the initial dose
Initial mean infant weight used in simulation (gm)	2988	2988
Simulated weight at cessation (gm)	2940	3010
Simulated dose at cessation (mcg)	27.1	18.1
Simulated normalized dose at cessation (mcg/kg)	9.3	6.1
Simulated % of infants who would require post cessation rescue dose	25%	39%
Actual % of infants in BBORN requiring post cessation rescue dose	N/A	44%
Actual median birthweight in BBORN (gm)	N/A	3040

#### *1.3.4.7 Terminal Extension of Dosing Interval*

In BBORN 44% of infants required a post cessation rescue dose of buprenorphine. The last administered dose was used for determination of the primary endpoint of length of treatment in the BBORN trial. Though the model suggests a lower rate of post dose cessation, the cessation dose is higher than in BBORN and remains relatively high. Rescue dose after a patient has cessation of medication is often seen as weaning “failure” by parents and some clinicians, rather than part of the weaning process. As the goal of this protocol is to explore alternate dosing regimens, the protocol will at the cessation or “bottom” dose switch over to a weaning of dose interval. This is represented in Figure 3 and below. The impact of this change in interval has not been formally simulated, but it is anticipated that this will reduce the number of post cessation rescue doses. The sample size of this trial will make formal assessment of this approach on clinical endpoints of length of treatment not possible, but the exercise will assist with exploration of regimen optimization.

Q8 dosing	Q12 dosing	Q24 dosing	Rescue doses if needed
Adjust dose	Adjust interval		

#### *1.3.4.8 Final Dose Regimen Selection*

Simulated regimens suggest additional efficacy when uptitration rate is extended from 30 to 50%, as well as decreased treatment duration when weaning rate is increased from 15 to 25%. In both cases, the larger

jumps reduce the discriminatory power of the regimen to avoid higher buprenorphine doses in infants who would have either been managed with lower dose of buprenorphine afforded by a slower uptitration, or those who would have benefited from a slower down titration rate. In addition, the incorporation of a new maximum dose is challenging to accurately capture using modeling techniques. As the goal of this protocol is to gather information to refine an existing model, it is prudent to undertake more modest dose and regimen changes.

### **1.3.5 *Efficacy Assessment of Length of Treatment***

Buprenorphine efficacy has been demonstrated in infants even with concentrations below the 0.7 ng/ml considered to be the level at which relief of adult abstinence symptoms begins. The model of Moore and Ng suggest the value in infants to be 0.8 ng/ml. Using the pharmacometric model used to describe the BBORN data, a simulation was created to predict the range of expected exposures associated with the proposed regimen. Compared to 5.3 mcg/kg, an initial dose of 8 mcg/kg would did not substantially change the mean number of titrations needed to reach stabilization, but did reduce the time to stabilization. The small sample size and lack of comparator group make an assessment of the endpoints of length of treatment, length of stay, or need for phenobarbital rescue within this study to be at best exploratory.

### **1.3.6 *Safety***

There has been no indication of idiosyncratic or dose-related toxicity. Respiratory related toxicity is of the largest concern with dosing of an opioid. In the BBORN trial there were no episodes of clinical respiratory depression. Model based analysis implied that at any time during the treatment period, the mean respiratory rate in morphine treated infants was lower by 4.4 breaths per minute (95% CI: 0.7, 8.1; p=0.020) as compared to buprenorphine treated infants in the same strata. Furthermore, in the pharmacometric modeling analysis there was no relationship between observed concentration of buprenorphine and respiratory rate. Hysteresis plots and patient-level data were also analyzed but showed no relationship between buprenorphine or norbuprenorphine concentration and respiratory rate. Considering the wide therapeutic index of buprenorphine in multiple populations, the modest increase in maximum dose is considered to have low risk for dose-dependent adverse effects.

## **1.4 *Pharmacogenetics Sample***

Pharmacogenetic variants can lead to differences to drug exposure. Since the primary endpoint of the trial is pharmacokinetic, a blood sample for pharmacogenetics will be obtained from infants enrolled. Pharmacogenetic variation in the neonatal abstinence syndrome has been primarily based upon differences in receptor polymorphisms such as OPMR1 or genes associated with neurotransmitter disposition such as

prepronociceptin (PNOC), catechol-O-methyltransferase (COMT) genes. There has not been demonstration of pharmacogenetic-linked drug metabolism or transport on outcomes in NAS. For this reason there will not be an a priori list of genes to be surveyed. In addition, the small number of patients to be enrolled will allow very limited power to differentiate drug exposure according to genotype. However, as the genetic analysis of the BBORN trial is currently underway, it is possible that there will be an emergent determinant of drug disposition based upon genotype.

## **2 STUDY OBJECTIVES**

### **2.1 Primary Objective**

To define buprenorphine pharmacokinetic exposure in infants treated with buprenorphine for neonatal abstinence syndrome (NAS) using a model-based optimized dose.

### **2.2 Exploratory Objectives**

- 1) To examine the safety of a model-based optimized dose of buprenorphine in neonates.
- 2) To estimate efficacy of length of treatment of a model-based optimized dose of buprenorphine for infants treated for NAS.
- 3) To evaluate possible developmental trajectory of urinary glucuronidated metabolites of buprenorphine.

## **3 OVERALL DESIGN AND PLAN OF THE STUDY**

### **3.1 Overview**

This is a single-site, open label clinical trial. Potential patients will be identified in the prenatal period by staff of the Thomas Jefferson University Family Center and by daily screening of the inpatient census at Thomas Jefferson University Hospital. Infants at risk for NAS will have abstinence assessed using the MOTHER scoring instrument, which is based upon Finnegan Score and will hereafter be called the “NAS score” (Appendix 1). This is the standard instrument used at Thomas Jefferson University Hospital. A need for initiation of treatment will be defined as any consecutive 3 scores adding up to  $\geq 24$  or any single score  $\geq 12$ , and the clinical decision of the attending physician that the infant requires pharmacologic therapy (Figure 2). When the threshold for initiation of treatment is reached, a re-review of inclusion and exclusion criteria will take place prior to dose administration. NAS scores will be obtained every 4 hours. Dose assessment will take place daily. If the three previous NAS scores are  $\geq 24$ , a dose advancement will take place (at the discretion of the neonatologist). Buprenorphine dose will be increased by 33% per uptitration. After two days of stability, patients will have weaning of dose until initial dose is reached.

## 3.2 Endpoints

### 3.2.1 *Pharmacokinetic Endpoint*

Sparse sampling will be used to generate an estimate of pharmacokinetic parameters and intersubject variability of sublingual buprenorphine. Population PK generated exposure profile of the revised dose schema will be compared to model simulations.

### 3.2.2 *Developmental Glucuronidation Endpoint*

Diaper cotton will be used to collect urine every 5-7 days. Glucuronidated buprenorphine metabolites will be assayed. The relative fraction of each glucuronidated metabolite will be reviewed as a function of postnatal age. Developmental phase 2 metabolic processes will be estimated on an exploratory basis using glucuronidated metabolites collected from spot urine.

### 3.2.3 *Safety Endpoint (exploratory)*

#### 3.2.3.1 *Adverse events*

Adverse events will be recorded in the patient's research chart using a standardized form. Events will be graded by blinded investigators. Adverse events will be graded by an investigator according to a severity score (mild, moderate, severe).

#### 3.2.3.2 *Serious adverse events*

A serious adverse event is one that results in death, permanent disability, prolongation of hospitalization, or judged by an investigator to be a significant medical event. All serious adverse events will be reported to the Institutional Review Board, and the FDA. An independent safety monitor will review all serious adverse events.

### 3.2.4 *Efficacy endpoints (exploratory)*

#### 3.2.4.1 *Length of Treatment*

Length of treatment is defined as the number of calendar days when treatment was initiated until the last dose of study drug using 12 midnight as the cut off between days. If feasible, hours of treatment from first until last dose of buprenorphine will be recorded.

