## 5 DRUG ADMINISTRATION REGIMEN

### 5.1 Identity

All study drug will be prepared in bulk solution, distributed to the patient ward, and unit dosed by nursing in 1 mL pediatric dispensing vials (Healthcare Logistics Cat. # 7870 or equivalent). Preparation and stability is listed in Appendix 2.

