### 5.2.2 *Phenobarbital*

The hospital standard of care phenobarbital elixir formulation (20 mg/5 ml or similar equivalent) will be used. Birth weight will be used for the calculation of phenobarbital loading and maintenance dose. A loading dose 20 mg/kg followed by daily oral dose of 5 mg/kg/day will be used. When buprenorphine is weaned to 50% of highest dose, phenobarbital is decreased to 2.5 mg/kg/day. After three additional opioid weans, phenobarbital will be discontinued and the buprenorphine weaned until cessation dose was met.

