## 8.2 Stopping Rules

No further enrollment will take place following a SAE judged to be probably or definitely related to study treatment. Following a related SAE, the independent safety monitor will review the adverse event and assess investigator designated causality. The safety monitor can request pharmacokinetic analysis for the affected infant if there is concern that the event was exposure related. Depending upon the clinical situation, options could include 1) continuation of study treatment with or without dose adjustment, 2) transition from buprenorphine to open label morphine, 3) transition from an opioid to phenobarbital monotherapy, or 4) cessation of all abstinence pharmacotherapy. This decision will be a consensus approach with the

investigator, with the input of the IRB in case of conflict between investigators and the safety monitor.

If an infant is withdrawn from the study, treatment will follow clinician guidance and will not be protocol-driven. However, such infants will be followed and will be included in safety analysis. There is no prespecified stopping rule for trial cessation. There is no predefined interim look for safety or efficacy.

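### Length of treatment ends at the last buprenorphine dose, so an infant moved to morphine or to phenobarbital alone scores a short course however long that treatment lasts

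*Protocol*

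**What the plan says.** Exploratory objective 2 (Protocol section 2.2) is to estimate length of treatment under the new regimen. Section 3.2.4.1 defines it as calendar days from initiation "until the last dose of study drug using 12 midnight as the cut off between days". Where feasible, "hours of treatment from first until last dose of buprenorphine will be recorded".

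Study drug is buprenorphine. The Synopsis lists only buprenorphine as study treatment, and section 5.1 says: "All study drug will be prepared in bulk solution, distributed to the patient ward". Phenobarbital is a separate, ordinary hospital product (section 5.2.2): "The hospital standard of care phenobarbital elixir formulation (20 mg/5 ml or similar equivalent) will be used". Morphine appears only as an alternative outside study treatment.

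Section 8.2 lists what may happen after a related serious adverse event. Besides continuing study treatment or stopping all abstinence drugs, the options include "2) transition from buprenorphine to open label morphine, 3) transition from an opioid to phenobarbital monotherapy". It adds: "If an infant is withdrawn from the study, treatment will follow clinician guidance and will not be protocol-driven". Of withdrawn infants it says that "such infants will be followed and will be included in safety analysis", and it does not mention the efficacy summary.

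**The concern.** The two sections do not fit together. Section 8.2 allows an infant to stop buprenorphine and still receive drug treatment for NAS, while section 3.2.4.1 stops counting at the last buprenorphine dose. Nothing in the protocol extends the count to replacement treatment, censors it at a switch, or marks the infant as not having completed. An infant switched in the first week could be treated for weeks more and still be recorded as one of the shortest courses in the trial.

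The trial has 10 infants and no comparator, so a single such value shows in the mean. Section 1.3.4.1 cites a BBORN mean of 15 days on buprenorphine, which is the natural figure to set beside the result. Section 1.1 says that the optimized dose could later be used in an efficacy trial.

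**Working it through.** There is no figure in the plan to reproduce: section 7.2 states that no formal power analysis was done, and no rate of switching is given. The check is a reading of the definition case by case, followed by an illustration of size.

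**Which infants are affected**

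- *Switched to morphine or to phenobarbital alone (section 8.2):* the count stops at the switch while NAS drug treatment goes on. The score is too short.
- *Withdrawn to clinician-guided treatment (section 8.2):* the same, if another NAS drug is given after buprenorphine.
- *All abstinence drugs stopped (section 8.2):* no later treatment is missed. The score is right.
- *Phenobarbital added at maximum buprenorphine dose (sections 3.2.4.3 and 6.8):* buprenorphine continues, so the count continues. Section 5.2.2 plans to stop phenobarbital before the buprenorphine wean is finished. Not affected.

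**Size for one switched infant**

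Inputs from the protocol: n = 10 (Synopsis); BBORN means of 15 days on buprenorphine and 28 days on morphine (section 1.3.4.1). Assumptions: the nine other infants average 15 days; the switch falls on day d, from 3 to 10; the whole course of NAS drug treatment lasts T days, from 15 to 28.

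- Mean as written = (9 × 15 + d)/10
- Mean counted to the end of all NAS drug treatment = (9 × 15 + T)/10
- Gap = (T − d)/10

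| d | T | As written | All NAS drugs | Gap (days) |
|---|---|---|---|---|
| 3 | 15 | 13.8 | 15.0 | 1.2 |
| 3 | 28 | 13.8 | 16.3 | 2.5 |
| 5 | 15 | 14.0 | 15.0 | 1.0 |
| 5 | 28 | 14.0 | 16.3 | 2.3 |
| 10 | 15 | 14.5 | 15.0 | 0.5 |
| 10 | 28 | 14.5 | 16.3 | 1.8 |

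The gap runs from 0.5 to 2.5 days, which is 0.5/15 = 3% to 2.5/15 = 17% of the BBORN mean. It depends only on T − d and the number of infants, not on the assumed 15 days for the others. Section 8.2 halts enrolment after a serious adverse event probably or definitely related to treatment, so the final number could be below 10 and the gap larger. With 5 infants, for illustration, it doubles to 1.0 to 5.0 days.

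**How often**

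The chance of at least one switch among 10 infants is 1 − (1 − p)^10. For assumed per-infant rates p of 2%, 5%, 10% and 20% this is 18%, 40%, 65% and 89%. Section 1.3.2 and Table 2 give some guidance on p: among 64 infants on buprenorphine in earlier trials, no adverse event was judged related. Zero of 64 has a one-sided 95% upper limit of 1 − 0.05^(1/64) = 4.6%. At that limit the chance of at least one among 10 is 1 − 0.954^10, or about 37%. For switches driven by related events, the 10% and 20% rates are therefore above what earlier experience supports. The limit covers neither the higher doses tested here nor withdrawal for other reasons.

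**If withdrawn infants were left out instead**

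With the nine others at 15 days, leaving the tenth out gives a mean of 15.0. The full mean would be 16.3 if that infant's course were 28 days, 15.0 if it were 15 days, and (9 × 15 + 10)/10 = 14.5 if it were 10 days. Exclusion can therefore shift the mean down, leave it unchanged or shift it up.

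**The case against.** The strongest reply is that this is a minor clarification. The listed switches follow a related serious adverse event, so they answer toxicity. Poor symptom control, the main form of efficacy failure that the protocol describes, is met by adding phenobarbital while buprenorphine continues, and the number of such infants is an endpoint in its own right (section 3.2.4.3). Section 1.3.5 calls length of treatment at best exploratory, and section 7.3 keeps the analysis descriptive. Length of stay runs to discharge and is not cut short by a switch. In 10 open-label infants a switch would be plain to see. BBORN also counted to the last administered dose (section 1.3.4.7), so a different end point could spoil the one comparison that readers will make.

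Most of this stands, and it rules out three stronger readings that a reader might infer:

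- *That the definition turns treatment failure into apparent efficacy.* Not as a general statement. Infants with inadequate control stay on buprenorphine and keep counting. Only withdrawal for other reasons could involve poor control, and the protocol describes no such case.
- *That withdrawn infants are kept for safety only.* Section 8.2 includes them in the safety analysis. It does not exclude them from efficacy.
- *That scoring switched infants short and leaving them out bias the result the same way.* The last step of the working shows that exclusion has no fixed direction.

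The objection does not remove the central point. The protocol states where the count ends and foresees treatment beyond that end, so this is a stated rule that can mislead, not a detail left to an analysis plan. The BBORN comparison is preserved if buprenorphine days are reported as well.

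**Conclusion.** The point holds within limits. Applied literally, section 3.2.4.1 gives a falsely short course to any infant who leaves buprenorphine for another NAS drug, a path that section 8.2 foresees. One such infant among 10 would lower the mean by about 0.5 to 2.5 days. That range rests on assumed switch days (3 to 10) and assumed total courses (15 to 28 days). The protocol gives no switch rate, and earlier experience suggests that switches after related events are uncommon.

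The primary pharmacokinetic endpoint is untouched, and so is every error rate, since no formal test is planned. The matter deserves correction because the remedy is cheap and a small descriptive mean has nothing else to offset the error.

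**What to change.** For this exploratory endpoint, amend section 3.2.4.1, and section 6.11 to match, as follows:

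1. Report length of treatment in all treated infants, from the first buprenorphine dose to the last dose of any drug given for NAS (buprenorphine, morphine or phenobarbital), including after a switch or withdrawal.
2. Report days on buprenorphine separately, as the figure to set beside BBORN.
3. Identify each switched or withdrawn infant, with the day of the switch and the total course.
4. Say in section 8.2 that withdrawn infants are included in the length-of-treatment summary as well as in the safety analysis.

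The cost is a few sentences. Withdrawn infants are already followed (section 8.2). Section 6.9 already collects dates and times of primary treatment and phenobarbital, and concomitant medication; the only check needed is that the last morphine dose is dated. The downside is small: the all-drug figure may be slightly longer than, and is defined differently from, the one reported for BBORN, which is why both figures are needed. No dose, switch, withdrawal or stopping rule changes.

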### **3.2.4.2 Length of Stay**

Length of stay is defined as the number of calendar days from date of birth to date of discharge from the hospital.

### **3.2.4.3 Need for Supplemental Phenobarbital Use**

Phenobarbital is used as a rescue therapy when maximum opioid replacement therapy dose is reached without adequate resolution of symptoms. The number of infants requiring phenobarbital rescue will be recorded.

## **3.3 Justification of Inclusion Criteria**

### **3.3.1 Preterm Infants**

Preterm infants have a well-described natural history of NAS and a need for treatment that differs from term infants. The Finnegan score does differ in preterm infants, but it remains the standard instrument for gauging withdrawal severity. The preterm population thus appears to differ from term infants in manifestations of disease. However, treatment approaches are similar and ~30% of infants at risk for NAS are premature. Barrett described the intravenous use of buprenorphine in 12 infants between the ages of 27-31 weeks with no safety issues identified. Hall reported infants 34 weeks and older in his descriptions of infants treated with buprenorphine in NAS. The buprenorphine treated infants in BBORN had a mean gestational age of 37.9 (SD 1.9). While inclusion of premature infants appears safe, this is a dose finding study with expected differential clearance based upon developmental stage. For this reason, the inclusion criteria will be widened slightly to  $\geq 36$  weeks. This will serve to expand the generalizability of data. Given the small sample size and few infants enrolled between 36-37 weeks, there likely will be only modest ability to detect maturation associated differences in drug exposure.

#### **3.3.1.1 Benzodiazepine Exposure**

A retrospective study at Thomas Jefferson University Hospital demonstrated that the length of NAS treatment for benzodiazepine exposed infants between 2000-2006 was prolonged, a finding confirmed in other reports. Hall reported 40% of buprenorphine treated infants as having been polysubstance exposed, though the exact break out of benzodiazepine exposures were not included. The unpublished MOP Plus trial at Thomas Jefferson University Hospital enrolled specifically infants with benzodiazepine exposure. [\[NCT01671410\]](#) No safety issues were identified in any of the six infants enrolled. There is not an anticipated pharmacokinetic interaction from in utero exposure. Inclusion of infants with benzodiazepine

exposure is thus safe and will increase the generalizability of findings.

## 4 STUDY POPULATION

### 4.1 Inclusion Criteria

Patients eligible for participation include:

1.  $\geq$  36 weeks gestation
2. Exposure to opioids in utero
3. Demonstration of signs and symptoms of neonatal abstinence syndrome requiring treatment

